6.2.1.1 Plan to protect PHI from improper use or disclosure

6.2.1.2 Plan to destroy identifiers or a justification for retaining identifiers

6.2.2 Explanation for why the research could not be practicably be conducted without access to and use of PHI

6.2.3 Explanation for why the research could not practicably be conducted without the waiver or alteration of authorization

6.3 Waiver or alteration of authorization statements of agreement

7.0 Study Design and Procedures

7.1 Study Design

Study Design: We plan to conduct a 7 week prospective, double blind, placebo controlled crossover study. Each patient, in a randomized design will receive three weeks of prazosin and three weeks of placebo separated by 1 week washout period. A 1-week washout period is considered sufficient, given that the half-life of prazosin is 2-3 hours, and previous studies have demonstrated that the clinical effects of prazosin are eliminated within a week^{10, 11}. The subjects

will be blinded and the randomization list will be sent directly to the research pharmacy. Methylcellulose will be used as placebo.

7.2 Study Procedures (PHASE A)

- Subjective Scales: EDI-3 (eating pathology), PCL –C (PTSD checklist- civilian version), CAPS (Clinician administered PTSD scale), PSQI (Pittsburg sleep quality index), HDRS (Hamilton Depression Rating Scale) & 5 relevant questions from sleep-50 questionnaire.
- Other parameters: Salivary Cortisol (5 diurnal samples), BMI, Vital signs, EKG, CMP, LFTs, UDS. Saliva samples will be analyzed in our departmental lab using ELISA kits (Alpco). Blood samples will be sent to Quest Diagnostics Lab for analysis. The Biological Safety and Recombinant DNA Committee registration number is FUM15-01p-2.
- Upon completion of the intervention period, participants will return to the Milton S. Hershey Medical Center and repeat the exact same procedures as completed during the Baseline period including the vital sign measurements, blood, urine, & saliva collection, sleep lab recordings, and questionnaire completion. Any unused medication and/or the empty medication bottle will be collected at the end of both interventions.

7.2.1 Day 1

The first day of the study will involve Consent, standard evaluation by therapist, if not done previously, initial blood draw, urine pregnancy test and EKG. Patients will be referred to cardiologist, if needed based on EKG results and will be excluded from the study.

7.2.2 Day 2

On the second day of the study participants meeting eligibility criteria based on EKG & labs, will be assessed by the psychiatrist and 5 diurnal salivary samples will be collected from the participants. Patients will be randomly assigned to one of the treatment arms. The two treatment arms with Prazosin and Placebo will be monitored similarly. Rating scales will also be collected by RA that day at baseline, as well as on the last day of the first and second treatment arms and the last day of washout period (Total 4 times). Vital signs will be checked that day and on each physician visit. Prazosin will be prescribed by the PI (psychiatrist) at 1 mg (taken by mouth once or divided BID) after the initial assessment on the second day of the study.

7.2.3 Weekly Visits

Symptoms will be reassessed and medication will be adjusted by 1-2 mg increments every 7 days based on clinical response and severity of night mares, to achieve maximum therapeutic benefit while monitoring adverse effects using side effects scale on weekly basis (psychiatrist will be using the scale at every visit). A phone contact by RA will be made on the morning after dose initiation and after each increment to monitor adverse events. The end point for capping the Prazosin dose will be 6 mg daily. The psychiatrist will administer adverse events rating scale and nightmare assessment using Sleep-50 Questionnaire at every psychopharmacologic

visit after initiation of medication in addition to the initial visit. Vital signs will be checked at each visit as well. The participants will have a total of 7 visits with the psychiatrist (1 for initial evaluation and 3 for the dose titration during each study arm). Research pharmacy and RA will determine and track the sequence and random allocation of the medication to ensure blind randomized trial. RA will also gather salivary samples from the patient at end of each study arm (5 diurnal samples for each arm) After 3 weeks on one treatment arm, a wash out period of 1 week will be given prior to starting the second study arm. The same sequence will be repeated for the second study arm and study questionnaires will be repeated on the last day of the washout period. Blood work will be drawn thrice, once at baseline and once at the end of each study arm. 5 Diurnal salivary samples will be collected thrice, once at baseline and once at the end of each study arm. All sets of cortisol level will be collected at the same time points as the baseline level to allow accurate comparisons. All Rating scales will be completed 4 times, once at baseline, once at end of wash out period and once at the end of each study arm. At the end of each study arm, any unused medication will be collected from the participant. Upon completion of the study, participants may want to continue taking the study medication if they experienced positive results. The PI will discuss with each participant if it is appropriate to continue taking the medication.

Study Procedures (PHASE B)

Objective Measure: PSG (Polysomnogram) will be conducted at baseline for 3 consecutive nights and the last 3 nights of each treatment arm for a total of 9 nights/ person during Phase B of the study. 2 participants will be enrolled in this phase. All other procedures will be the same as described under Phase A.

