4.2 Recruitment process

The research assistant will contact the participants to obtain consent and avoid any form of coercion from healthcare providers. The research assistant will get verbal consent via phone and schedule the patient for consent discussion, therapist evaluation (if not already in medical record), the screening lab work, pregnancy test, Salivary Cortisol collection, BMI, Vital signs, CMP, LFTs, UDS & EKG.

Informed consent will be obtained at the GCRC by the Research Assistant.

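### Section 7.2.3 gives the research assistant a part in setting and following the treatment order, the same role collects the primary scale, and the plan neither blinds that role nor names the CAPS rater

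*Combined protocol and SAP*

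**What the plan says.** Section 7.1 sets the design: "We plan to conduct a 7 week prospective, double blind, placebo controlled crossover study". It says that subjects are blinded and that "the randomization list will be sent directly to the research pharmacy". It does not identify the second blinded party, and it does not say who produces the list or that the pharmacy is its only holder.

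Section 7.2.3 then says: "Research pharmacy and RA will determine and track the sequence and random allocation of the medication to ensure blind randomized trial". Section 24.1.3 adds only that the random numbers come from a computer. Section 24.1.5, on blinding, deals with capsule size and with no person.

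The RA has several other tasks:
- Consent (4.2): "Informed consent will be obtained at the GCRC by the Research Assistant".
- Scales (7.2.2): "Rating scales will also be collected by RA that day at baseline", and again at the end of each arm and of the washout, four times in all.
- Safety calls (7.2.3): "A phone contact by RA will be made on the morning after dose initiation and after each increment to monitor adverse events".
- Saliva for cortisol at the end of each arm (7.2.3).

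Section 7.2 lists "CAPS (Clinician administered PTSD scale") among the subjective scales, and section 9.1 takes its distressing dream item as the primary measure.

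**The concern.** Someone who helps to set the treatment order knows it. Followed as written, section 7.2.3 gives that knowledge to the role that collects a subjective primary outcome and speaks to patients about side effects after each dose change. Identical capsules protect the patient's blind. They do nothing about a staff member who already has the sequence.

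Each patient is compared with herself, so what matters is whether ratings are obtained differently in the two arms. Phase A also decides whether Phase B goes ahead (1.1), and section 2.3 intends the results to support a fully powered trial. Ratings collected by someone who knew the order cannot be re-collected blind afterwards.

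**Working it through.** The plan gives no figure on this point to reproduce, so the check sets the sections side by side.

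**1. Who can know the sequence?** Under 7.1, the pharmacy, plus an unnamed producer of the list. Under 7.2.3, the pharmacy and the RA. Under 24.1.3, no one is named. The RA's access appears only in 7.2.3, but it is stated there as a procedure.

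**2. Who is blinded?** By name, only the subjects (7.1). Sections 24.1.5 and 24.1.6.3 describe over-encapsulation and the placebo filler. No section says that the RA works from coded bottles. The closing words of the 7.2.3 sentence state an aim and give no mechanism. No section gives the psychiatrist the sequence.

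**3. Who rates the CAPS at the outcome times?**
- 7.2 labels the scale as administered by a clinician, while 7.2.2 has the RA collect the scales.
- 4.4 uses the distressing dreams item within the therapist's screening, which concerns eligibility.
- 4.1 says in general that the psychiatrist does the evaluations at the GCRC.
- 7.2.3 has the psychiatrist administer the adverse events scale and the Sleep-50, and does not mention the CAPS.
- The Phase A schedule in 7.3 puts the post-baseline rating scales on Day 7 of weeks 3, 4 and 7, with no psychiatrist visit on those days.

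The rater therefore cannot be identified.

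**4. How would a shift reach the result?** Let δ be the true prazosin-minus-placebo difference on the CAPS item. Let b be the average difference between arms that arises only because someone involved in the rating knew the treatment. The expected observed difference is then

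E(D) = δ + b.

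Section 9.2 plans t-tests and a mixed model with period and sequence terms. Because b moves with treatment, neither term removes it. Only the sum δ + b can be estimated, and more patients do not shrink b. If b = 0 there is no harm. The documents give no value for b, so I attach none.

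**5. How many ratings are exposed?** There are four rating times per patient (7.2.2).
- Phase A, 8 patients (1.1): 8 × 4 = 32 ratings, of which 8 × 2 = 16 are the end-of-arm ratings being compared.
- All 10 patients, as in 9.1: 10 × 4 = 40, of which 10 × 2 = 20.

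**6. Is there an independent check?** Cortisol is a laboratory assay, but the RA gathers the saliva. The Sleep-50 questions are among the scales the RA collects, so only the psychiatrist's own Sleep-50 at visits is separate. In the 7.3 schedule its last use in each arm is Day 1 of week 3 or 7, six days before the Day 7 ratings. Neither measure is the primary item.

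**The case against.** The strongest reply is that the two sections need not contradict each other. Section 7.1 says where the list is sent, not who makes it or who else may see it. A list made by the RA and sent to the pharmacy would satisfy that sentence. The 7.2.3 sentence has blinding as its stated purpose, so tracking by code may be what was meant. This stands in part: 'not reconciled' is the right description, and a flat contradiction is not shown. But the text has the RA involved in setting the order, and nothing describes a code.

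A reader might also infer that an unblinded RA scores the primary outcome. The documents do not say so. They say that the RA collects the scales, they label the CAPS as clinician administered, and 4.1 gives the evaluations to the psychiatrist. Section 7.2 also has participants "repeat the exact same procedures as completed during the Baseline period" after the intervention, which might imply a repeated clinician assessment. The 7.3 schedule shows none on the rating days, so the rater remains unknown in either direction.

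It is tempting to put an inflated type I error rate on this. Any such figure would need an assumed shift, an assumed share of affected patients and a standard deviation for the no-effect case. The plan supplies none of the three, so the figure would be invented.

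Finally, every patient receives both treatments, so the RA's role in consent makes allocation concealment a minor point. That is correct. The crossover does not, however, remove a difference in assessment between arms.

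**Conclusion.** Wrong as written. The plan states a procedure that gives the treatment order to the role that collects the primary scale, in a trial it calls double blind, with no safeguard described for that role and no named CAPS rater. Blinded assessment of the primary outcome is not assured; the documents do not show that it fails. The subjects' masking is unaffected, and nothing indicates that the psychiatrist is unblinded.

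The extent is all 32 Phase A ratings, or 40 for ten patients, of which 16 or 20 feed the treatment comparison. The size of any bias is unknown and may be zero. For bias in the CAPS item to arise, the RA would have to rate it, or influence the rater or the patient, and that knowledge would have to change the ratings. The finding rests on the text and on the fact that such a shift could not be separated from δ afterwards.

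**What to change.** 1. **7.2.3:** remove the RA from the allocation sentence, so that only the research pharmacy holds and tracks the sequence.
2. **24.1.3:** state that the list is generated by the pharmacy, or by someone with no consent, patient-contact or outcome role.
3. **7.1:** state that the RA, the psychiatrist/PI and whoever rates the CAPS are blinded, as well as the subjects.
4. **7.2.2:** name the existing team member, without access to the sequence, who administers the CAPS at all four rating times, consistent with its clinician-administered label. The plan does not show a second RA kept from the sequence, so that should not be presumed.

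**Cost.** This is a wording amendment; the pharmacy already receives the list and prepares the capsules. If the RA now generates the list, that one-off task moves to the pharmacy. If a clinician is named as rater, the baseline rating falls on the psychiatrist's Day 2 assessment, leaving up to 4 − 1 = 3 added interviews per patient: at most 3 × 8 = 24 in Phase A, or 3 × 10 = 30 for all ten.

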7.3 Duration of Participation

The study duration is 7 weeks.

Phase A (No PSG Recordings)

		Day 1	Day 2	Day 3	Day 4	Day 5	Day 6	Day 7
Screening	Consent	x						
	Blood Collection, Urine Pregnancy Test, &EKG	x						
	Standard Evaluation by Therapist	x						
Baseline Procedures	Psychiatric Assessment & Randomization		x					
	Saliva Collection (8a, 12p, 3p, 6p, 9p)		x					
	Rating Scales (RS) and Vitals		x					
	Start Treatment		x					
Intervention Arm 1	Week 1	Psychiatrist Visit	x					
		Vitals, Adverse Event Rating Scale (AERS), Sleep-50	x					
		Research Assistant Phone Call		x				
	Week 2	Psychiatrist Visit	x					

		Vitals, AERS, Sleep-50	x						
		Research Assistant Phone Call		x					
	Week 3	Psychiatrist Visit	x						
		Vitals, AERS, Sleep-50	x						
		Research Assistant Phone Call		x					
		Saliva/Blood Collection & RS							x
Washout	Week 4	Rating Scales							x
Intervention Arm 2	Week 5	Psychiatrist Visit	x						
		Vitals, AERS, Sleep-50	x						
		Research Assistant Phone Call		x					
	Week 6	Psychiatrist Visit	x						
		Vitals, AERS, Sleep-50	x						
		Research Assistant Phone Call		x					
	Week 7	Psychiatrist Visit	x						
		Vitals, AERS, Sleep-50	x						
		Research Assistant Phone Call		x					
		Saliva/Blood Collection & RS							x

Phase B (2 subjects have PSG Recordings)

			Day 1	Day 2	Day 3	Day 4	Day 5	Day 6	Day 7
Screening	Consent		x						
	Blood Collection, Urine Pregnancy Test, &EKG		x						
	PSG Recording				x				
	Standard Evaluation by Therapist		x						
Baseline Procedures	Psychiatric Assessment & Randomization			x					
	Saliva Collection (8a, 12p, 3p, 6p, 9p)			x					
	Rating Scales (RS) and Vitals			x					
	PSG Recordings					x	x		
	Start Treatment							x	
Intervention Arm 1	Week 1	Psychiatrist Visit	x						
		Vitals, AERS, Sleep-50	x						
		Research Assistant Phone Call		x					
	Week 2	Psychiatrist Visit	x						
		Vitals, AERS, Sleep-50	x						
		Research Assistant Phone Call		x					
	Week 3	Psychiatrist Visit	x						
		Vitals, AERS, Sleep-50	x						
		Research Assistant Phone Call		x					
		Saliva/Blood Collection & RS							x
		PSG Recordings					x	x	x
Washout	Week 4	Rating Scales							x
Intervention Arm 2	Week 5	Psychiatrist Visit	x						

		Vitals, AERS, Sleep-50	x						
		Research Assistant Phone Call		x					
Week 6		Psychiatrist Visit	x						
		Vitals, AERS, Sleep-50	x						
		Research Assistant Phone Call		x					
Week 7		Psychiatrist Visit	x						
		Vitals, AERS, Sleep-50	x						
		Research Assistant Phone Call		x					
		Saliva/Blood Collection & RS							x
		PSG Recordings					x	x	x

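### The only pregnancy test the plan names is at Day 1 screening, so Phase A placebo-first patients first take prazosin 29 days later with no named retest

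*Combined protocol and SAP*

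**What the plan says.** A pregnancy test is named in three places, and all three describe the same screening test:

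- Section 4.2 lists "the screening lab work, pregnancy test, Salivary Cortisol collection, BMI, Vital signs, CMP, LFTs, UDS & EKG" among the procedures to be scheduled.
- Section 7.2.1 (Day 1) lists "initial blood draw, urine pregnancy test and EKG".
- Both schedules in section 7.3 have one screening row, "Blood Collection, Urine Pregnancy Test, &EKG", marked on Day 1 only. No row for Weeks 1 to 7 names the test.

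In Phase A treatment begins "after the initial assessment on the second day of the study" (section 7.2.2). The Phase B schedule starts treatment on Day 6. Section 7.1 sets three weeks per treatment with one week of washout between them, and section 24.1.3 leaves the order to randomization.

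One sentence in section 7.2 may imply a later test. On completing the intervention period, participants are to "repeat the exact same procedures as completed during the Baseline period including the vital sign measurements, blood, urine, & saliva collection". It does not say what the urine is tested for.

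Pregnancy is an exclusion in section 3.2, and section 12.0 repeats it. Section 12.0 also requires contraceptive precautions, a discussion with the investigator, and immediate notification if pregnancy is suspected. It describes the risk to an unborn baby as largely unknown, with some animal studies suggesting harm, and notes that limited use in pregnant women has shown no abnormalities.

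**The concern.** In a crossover, half of the sequences do not meet the active drug until the second period. A single entry test therefore sits close to first exposure for one sequence and far from it for the other. Here the plan checks its own exclusion the day before first prazosin in the Phase A prazosin-first sequence, and about a month before it in the placebo-first sequence. It gives no reason for the difference.

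What is at stake is first exposure of an unrecognized pregnancy to a drug whose fetal risk the protocol calls largely unknown. Nothing in the estimation or testing of the treatment effect depends on it.

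**Working it through.** **Inputs.** Pregnancy test on Day 1 (7.2.1, 7.3). Treatment start on Day 2 in Phase A (7.2.2, 7.3) and Day 6 in Phase B (7.3). Each arm lasts 21 days and the washout 7 days (7.1).

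**The plan's own figure.** 3 + 1 + 3 = 7 weeks, which matches the duration in section 7.3.

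**Formulas.** With S the start day, arm 1 runs from S to S + 20, washout from S + 21 to S + 27, and arm 2 starts on S + 28. The gap is the day of first prazosin minus the day of the last test.

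| | Phase A (S = 2) | Phase B (S = 6) |
|---|---|---|
| Arm 1 | Days 2-22 | Days 6-26 |
| Washout | Days 23-29 | Days 27-33 |
| Arm 2 starts | Day 30 | Day 34 |
| Gap, prazosin first | 2 - 1 = 1 day | 6 - 1 = 5 days |
| Gap, placebo first | 30 - 1 = 29 days | 34 - 1 = 33 days |
| Difference between sequences | 29 - 1 = 28 days | 33 - 5 = 28 days |
| Placebo-first gap if urine at end of arm 1 is a pregnancy test | 30 - 22 = 8 days | 34 - 26 = 8 days |
| Placebo-first gap with a test at Week 4 Day 7 | 30 - 29 = 1 day | 34 - 33 = 1 day |
| Placebo-first gap with a test at Week 5 Day 1 | 0 days | 0 days |

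**Sensitivity to the calendar.** The Phase A figure takes Day 2 as Week 1 Day 1. Moving that alignment by one day either way gives 28 to 30 days. If Days 1 and 2 are not consecutive calendar days, both sequences' gaps lengthen equally: 29 becomes a minimum and the 28-day difference stays.

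**What the urine repeat could be.**

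- *Which test.* Day 1 includes a urine pregnancy test, but the parameter list in 7.2 reads "Salivary Cortisol (5 diurnal samples), BMI, Vital signs, EKG, CMP, LFTs, UDS". It contains a urine drug screen (UDS) and no pregnancy test. Either test, or both, would fit.
- *When.* The sentence refers to the intervention period in the singular. The repeat could follow each arm or come only at the end of the study. In the latter case the gap stays at 29 days.
- *Schedules.* The end-of-arm rows list saliva, blood and rating scales but no urine. They also omit UDS and BMI, so a missing row is weak evidence.
- *Section 7.2.3.* It counts repeats for blood ("Blood work will be drawn thrice, once at baseline and once at the end of each study arm"), for saliva (also three) and for scales ("All Rating scales will be completed 4 times, once at baseline, once at end of wash out period"). It gives no count for urine. This says more than a missing row, because it counts the other two specimens one by one, but it gives no count for EKG or BMI either.

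**Patients affected.** Assuming 1:1 allocation (the ratio is not stated), about 8 / 2 = 4 in Phase A and 2 / 2 = 1 in Phase B. Phase B runs only if Phase A shows a signal of efficacy.

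**The case against.** The best counter-argument is that the plan already implies a retest. Section 7.2.3 counts the first blood draw as baseline, and the schedule puts that draw on Day 1, so the baseline procedures to be repeated can be read to include the Day 1 pregnancy test. Urine is grouped with blood and saliva, which are both collected at the end of each arm. The same paragraph of 7.2 collects unused medication after both interventions. On this reading the gap is 8 days and the defect is loose drafting.

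That reading is reasonable and cannot be ruled out. It does not close the point. The test would still precede the washout, leaving 8 days before first prazosin, and no text makes arm 2 dispensing depend on a negative result. Staff following the schedule would also find no urine row to act on.

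Three further objections have merit:

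- The day counts assume consecutive study days. Eligibility on Day 2 depends on Day 1 EKG and laboratory results, and blood goes to an outside laboratory, so consecutive days are doubtful. Any delay lengthens the gaps and does not remove the asymmetry.
- The safeguards in section 12.0 are real, and a psychiatrist sees every participant at Week 5 Day 1. They make the absolute risk small. However, self-report works only once a participant suspects pregnancy, and no test is named for that visit.
- Prazosin-first patients also take the drug for 21 days with no named test during the arm. One test before arm 2 would not cover conception during an arm in either sequence.

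**Conclusion.** The concern holds as a minor safety point. The plan names one pregnancy test, at Day 1. In Phase A it precedes first prazosin by 1 day in one sequence and 29 days in the other; in Phase B by 5 and 33 days. The most favorable reading of section 7.2 shortens the placebo-first gap to 8 days in both phases.

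These figures rest on consecutive study days and on the stated arm and washout lengths. The count of about 4 women in Phase A and 1 in Phase B rests on equal allocation. No bias or loss of power follows, and the expected harm is small.

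**What to change.** 1. Add a urine pregnancy test for both sequences, either at Week 4 Day 7, when rating scales are already scheduled, or at the Week 5 Day 1 psychiatrist visit.
2. Require a negative result before arm 2 capsules are dispensed. Withdraw a participant with a positive result as a safety concern under section 3.3.1.
3. State in section 7.2 which urine tests are repeated (pregnancy test, UDS or both), and whether after each arm or only at the end of the study.

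Testing both sequences alike leaves the blind unaffected. The cost is 8 × 1 = 8 tests in Phase A and 8 + 2 = 10 in total if Phase B runs, all at an existing visit. The document changes are one row in each schedule, the dispensing condition and one clarified sentence in section 7.2.
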